****Revised/additional exclusion criterion added on IRB's instruction, effective 08/07/2020 through the end of study****

- 19) Patients with diabetes

Rationale: For the duration of the COVID-19 pandemic, patients with diabetes, who are increased risk of serious complications from COVID-19 exposure, will be excluded.

Statistical Considerations and Statistical Analysis Plan

Sample Size

150 depressed adults will be enrolled in the study and randomized to one of the three treatment arms: ketamine + cognitive training (n=50); ketamine + sham training (n=50); or saline + cognitive training (n=50). Enrollment will continue until a final sample is acquired that includes the full target of n=150 patients who complete, at a minimum, (1) an infusion day, (2) a 24-hour assessment visit, and (3) $\geq 75\%$ of intended Neurocognitive Training (active or sham NT) visits, and will thus be considered to have received their NT allocation.

Power Analyses

Previous studies comparing intravenous ketamine to inert and psychoactive comparators (e.g., midazolam) report large effects at 24-hours ($d=.80$ for depression; $d>3$ for brain activation). The PI's previous mechanistic CT study in depression found large effects ($d=.7-1.0$) on symptom and performance-based cognitive measures. Clinically, we are interested in observation of moderate-large effects. The proposed design will yield 80% power to detect moderate effects based on comparisons of 100 ketamine and 50 saline patients ($d\geq .49$ and $r\geq .31$ using $\alpha=.05$). Based on comparisons of 50 patients in each of the ketamine+CT, ketamine+sham, and saline+CT conditions and 80% power, effects of $d\geq .57$ will be detectable (using $\alpha=.05$). Power for primary mixed effects analyses comparing treatment groups, which increases with additional repeated measures, will be higher than for such post-hoc single-point contrasts.

Analytic Plan

Infusion Phase. Mixed models regression with timepoint (baseline, infusion+24-hours) as a continuous within-subject factor, drug condition (ketamine vs. saline) as a fixed between-subject factor, and subject as a random factor will be applied to test hypothesized time*drug interactions on outcomes. For outcomes where time*drug interactions are observed, direction of effects within each drug condition will be disambiguated using baseline vs. post-infusion contrasts.

Neurocognitive Training Phase. Mixed models regression with timepoint (24-hrs to 30 days) as a continuous within-subject factor, condition (ketamine+NT, ketamine+sham, saline+NT) as a fixed between-subject factor, and subject as a random factor will be applied to test hypothesized treatment and time*treatment interactions on outcomes. Saline+CT will serve as the reference group to test for enduring (main) effects of treatment and for time*treatment interactions.

Exploratory analysis 1 will extend mixed models analysis of depressive symptoms into the 12-month naturalistic follow-up using self-report (primary self-report outcome=QIDS-SR).

Exploratory analysis 2 will utilize a validated data-driven approach to identify integrative/combined moderators of CT effects (DV=MADRS slope), quantified as the optimal weighted combination of moderators (via elastic net w/cross-validation) across all primary + exploratory indices (e.g., fMRI, HNK/BDNF levels, etc.) assessed after ketamine (n=100), defining the data-driven, integrative brain state that optimizes benefit from CT.

Sensitivity analyses will be applied to all hypotheses to explore the impact of main and moderating effects of key biological variables: sex (stratified at randomization to ensure ~60%

female within-cell), age; and baseline clinical variables: treatment-resistance (stratified), concurrent medication.

Exploratory analyses will probe for generalization to other neurocognitive indices and self-report measures [e.g., depressive schemas (CTI); PROMIS measures; QIDS-SR; WHO Disability Assessment Scale].

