discontinuation and the rarity of follow-up opportunities in community practice. A more integrative model of ketamine's impact—in particular, anticipated increases in flexible processing across cognition, information processing, and neural networks—reveals a previously unforeseen opportunity to test for synergistic effects when ketamine is coupled with a brief, automated cognitive training intervention designed to consolidate beneficial forms of cognitive processing while neuroplasticity is high. Thus, this project will push the boundaries of how rapid-acting agents could be used clinically, i.e. as short-term cognitive flexibility enhancers. Here, rapid-acting pharmacology becomes merely the first step in a novel treatment algorithm designed to foster relief that is both rapid and durable, simultaneously taking advantage of technology's potential for low-cost, portable, safe, dissemination-ready intervention. Consistent with findings suggesting gold-standard behavioral treatments can prevent depression relapse in the absence of ongoing care, and preliminary evidence that brief cognitive training approaches can likewise have enduring effects over 1-year, we propose that the introduction and facilitation of new learning during a ketamine-induced window-of-opportunity will provide an efficient path to relief that is both rapid and enduring.

Study Objectives

This project seeks to identify the neural and cognitive changes that accompany rapid relief from depressive symptoms following intravenous ketamine. We will then test whether these changes promote the uptake of helpful information delivered by a computer-based training protocol. This work could ultimately lead to the ability to treat depression more efficiently by rapidly priming the brain for helpful forms of learning.

Study Design & Methods

This study is a randomized, double-blind, parallel arm, controlled trial. A target sample size of 150 patients exhibiting the target deficits (negative self-representations and elevated depressive symptoms) will be randomized 2:1 to intravenous ketamine (0.5mg/kg) or saline, followed by either a computer-based cognitive training protocol designed to implicitly instill positive self-representations via Evaluative Conditioning (n=100 drawn from either the ketamine or saline groups) or a sham variant (n=50, from the ketamine group only). Both males and females age 18-60 will be enrolled.

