- General demographic and medical history forms
- Medical intake and comprehensive screening assessments performed by clinical research staff at Bellefield Towers or [name] (Oxford Building). Findings will be reviewed for eligibility and signed by a board-certified physician co-investigator ([name]) prior to the infusion. A drug test will also be obtained at intake; urine pregnancy tests may be obtained prior to fMRI scans at the MRRC.

Screening/baseline procedures include pre-infusion psychiatric evaluation, medical screening, and assessment battery (depression/emotional functioning assessments, neuroimaging, cognitive tasks)=1-2 visits over approximately 1-3 weeks

Infusion (ketamine or saline) visit (“Intervention Day 1” in consent form)=one visit, completed within approximately 1 week of baseline assessments

24-hours post-drug assessment battery (“Intervention Day 2” in consent form) (depression/emotional functioning assessments, neuroimaging, cognitive tasks)=one visit completed 24-hours after drug infusion

Cognitive training sessions and brief assessment battery (“Intervention Days 2,3,4,5” in consent form) (depression and suicidality assessments)=eight 15-20min sessions completed 2x/day (sessions separated by >=20 min) on days 1-4 post-infusion

Infusion +5-days assessment battery (“Intervention Day 6” in consent form) (depression/emotional functioning assessments, neuroimaging, cognitive tasks)=one visit completed following completion of all cognitive training sessions

Infusion +7 days remote (questionnaire) assessment (depression assessments)

Infusion +12 days assessment battery (depression/emotional functioning assessments, cognitive tasks)

Infusion +21 days remote (questionnaire/phone) assessment (depression and suicidality assessments)

Infusion +30-days assessment battery (depression/emotional functioning assessments, neuroimaging, cognitive tasks)

Infusion +2, 3, 4, 5, 6 & 12-months remote, naturalistic follow-up assessments (depression/emotional functioning assessments)=questionnaires completed monthly 2-6 months post-infusion and then once more at 12-months follow-up

Total duration of acute study period (after screening is completed)=approximately 4-5 weeks. Includes 1 infusion visit, 5 in-person assessment visits, 2 remote assessments, and 8 brief cognitive training sessions (twice-daily for 4 days post-drug infusion).

Total duration of naturalistic follow-up period=1-year.

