5) Acute suicidality or other psychiatric crises requiring treatment escalation. We will use the Columbia-Suicide Severity Rating Scale (C-SSRS; Version 1/14/09) as both an initial exclusion criteria (C-SSRS “Baseline/Screening” Version for past 1-month period) and as grounds for rescue/removal (C-SSRS “Since Last Visit” form). The C-SSRS will be administered using a paper form by an experienced and thoroughly trained clinical assessor on the study team. Subjects with C-SSRS suicide ideation scores scored “yes” on items 4 (active suicidal ideation with some intent to act) and/or 5 (active suicidal ideation with specific plan and intent) will be excluded from the study, and if enrolled, will be exited from the study and referred immediately

to the nearest emergency mental health facility for additional thorough assessment and appropriate treatment referral.

- 6) Changes made to treatment regimen within 4 weeks of baseline assessment
- 7) Reading level <6th grade as per patient self-report
- 8) For study entry, patients must be reasonable medical candidates for ketamine infusion, as determined by a board-certified physician co-investigator during study Screening. Serious, unstable medical illnesses including respiratory [obstructive sleep apnea, or history of difficulty with airway management during previous anesthetics], cardiovascular [including ischemic heart disease and uncontrolled hypertension], and neurologic [including history of severe head injury] will be exclusions.
- 9) Clinically significant abnormal findings of laboratory parameters [including urine toxicology screen for drugs of abuse], physical examination, or ECG.
- 10) Uncontrolled or poorly controlled hypertension, as determined by a board-certified physician co-investigator's review of vitals collected during screening and any other relevant medical history/records.
- 11) Patients with one or more seizures without a clear and resolved etiology.
- 12) Patients starting hormonal treatment (e.g., estrogen) in the 3 months prior to Screening.
- 13) Past intolerance or hypersensitivity to ketamine.
- 14) Patients taking medications with known activity at the NMDA or AMPA glutamate receptor [e.g., riluzole, amantadine, memantine, topiramate, dextromethorphan, D-cycloserine], or the mu-opioid receptor.
- 15) Patients taking any of the following medications: St John's Wort, theophylline, tramadol, metrizamide
- 16) Patients who have received ECT in the past 6 months prior to Screening.

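### Does giving 150 both as the number randomised and as the number completing the training rule, with no named analysis set, require a change to the plan?

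*Combined protocol and SAP*

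**What the plan says.** Study Design & Methods states: "A target sample size of 150 patients exhibiting the target deficits (negative self-representations and elevated depressive symptoms) will be randomized 2:1" to ketamine or saline. The Sample Size section repeats the figure: "150 depressed adults will be enrolled in the study and randomized to one of the three treatment arms", with 50 in each. The next sentence sets the recruitment stop: "Enrollment will continue until a final sample is acquired that includes the full target of n=150 patients who complete, at a minimum" an infusion day, a 24-hour visit and at least 75% of training visits. It adds that such patients count as having received their training allocation.

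The data collection timeline describes the training as "eight 15-20min sessions completed 2x/day (sessions separated by >=20 min) on days 1-4 post-infusion". Exclusion criterion 5 says that patients who meet the stated C-SSRS items "will be excluded from the study, and if enrolled, will be exited from the study and referred immediately".

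The Power Analyses section works "based on comparisons of 100 ketamine and 50 saline patients" and from 50 per arm in the three-arm contrasts. Exploratory analysis 2 uses indices "assessed after ketamine (n=100"). The Analytic Plan gives the terms of the infusion-phase and training-phase mixed models but does not say which patients enter them. No section gives an expected drop-out rate or a cap on the number randomised.

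**The concern.** Taken literally, 150 randomised and 150 meeting the rule agree only if every randomised patient meets it. Otherwise more than 150 are randomised, and the reader cannot tell how many.

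The larger worry is the analysis population. The only final sample described is tied to completion, and completion is settled after randomisation. For the infusion phase it is also settled after the outcome: 75% of training is 3 of 4 days or 6 of 8 sessions, so it cannot be reached before day 3, about two days after the 24-hour assessment. If only those 150 were analysed, both phases would compare groups selected after randomisation. At least one exit route on those days, the C-SSRS criterion, is linked to severity. If patients who do worse are more likely to leave, and more of them are on saline, the completers would understate a true ketamine effect.

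**Working it through.** **1. The plan's own power figures.** Inputs from Power Analyses: 100 vs 50, 50 vs 50, α=0.05 (taken as two-sided), 80% power. The normal approximation is d = (1.960+0.842)·√(1/n₁+1/n₂).
- 100 vs 50: 2.802 × √(0.01+0.02) = 0.485; the noncentral t gives 0.488 (stated 0.49).
- 50 vs 50: 2.802 × √(0.02+0.02) = 0.560; the noncentral t gives 0.566 (stated 0.57).

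Both reproduce. They require 150 analysed patients, which the recruitment rule protects.

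**2. Number randomised.** N = 150/(1−f), where f is the share failing the rule. No f is given, so it is assumed.

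| f | N |
|---|---|
| 5% | 158 |
| 10% | 167 |
| 15% | 177 |
| 20% | 188 |

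**3. Do the counts point to a completer analysis?** The figures 100/50 and 50/50/50 fit 150 completers. They fit 150 randomised equally well: Study Design & Methods uses the same counts to justify the allocation ratio. They do not separate the two readings. The word *includes* allows a final sample larger than the 150. The stated consequence of the rule concerns receipt of training and is not linked to the infusion-phase model, which needs only baseline and 24-hour data.

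**4. Size of the harm if only completers were analysed.** Assumptions: scores with SD 1 at each time; one logistic drop-out mechanism shared by both arms, slope 0.5–1.0 per SD of severity; 10–20% lost overall; true d=0.49; simulation with 1 million per arm.

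24-hour mean, drop-out driven by 24-hour level:
- The mean difference falls by 0.01–0.06 SD.
- Losing the worst patients also narrows the spread. In the worst case (20%, slope 1.0) the difference is 0.49−0.059 = 0.431 and the completers' SD is 0.942, so the standardised effect is 0.431/0.942 = 0.458.
- Power for 100 vs 50 at 0.458 is about 75%. Over all scenarios it is about 75–80%, against 80% without selection.
- At d=0.80, the 24-hour depression effect cited in Power Analyses, power stays at about 99%.

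Time-by-drug interaction, as change from baseline with assumed correlation 0.3–0.6:
- The bias is 0.004–0.040 SD if drop-out follows 24-hour level, and about 0.01–0.07 SD if it follows change.
- In the worst case power falls from 66% to about 59–60% at correlation 0.3, and from 88% to about 85% at 0.6.

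**5. The relevant loss is narrower.** For the 24-hour test, the selection that matters affects patients who attended at 24 hours and then missed the training threshold. With 3% lost there (assumed), the bias on the 24-hour mean is at most about 0.015 SD and power is 79–80%.

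**6. Training phase.** If share f of an arm is lost and non-completers differ from completers by g SD, that arm's completer mean shifts by f·g. The bias between two arms is (f₁−f₂)·g. With 15% vs 5% lost and g=0.3–0.5 (assumed), it is 0.10×0.3 = 0.03 to 0.10×0.5 = 0.05 SD. With equal loss and equal g it is zero.

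**The case for a change.** The strongest case for a change is that a mixed model uses all available data only from patients who are put into it, and the plan does not say who is. Replacing drop-outs restores the count but not the randomised comparison. A sentence naming the set would cost nothing and would remove a later choice of population. The statement that no set is named is correct, and so is the statement that the expected number randomised is missing.

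The size can also be made to look larger in two ways. First, subtracting the worst bias from d gives 0.49−0.06 = 0.43 and 69% power. That leaves the SD at 1, although the same drop-out shrinks it; with both effects counted, power is about 75%. Second, if 10–20% were lost at random from the worse half of saline and nobody from ketamine, the bias on the 24-hour mean would be f×0.798/(1−f), or 0.09–0.20 SD. This is an extreme pattern for a double-blind trial, and nothing in the documents suggests it. The one severity-linked exit they describe rests on C-SSRS items that already exclude patients at entry.

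What stands is that a mechanism differing by arm could push the bias either way, and that the documents give no rate to rule it out. That matters only under an analysis that the plan does not propose.

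**Conclusion.** The concern identifies a real silence but not a fault in the plan. The target of 150 and the completion rule form a recruit-until-target scheme, in which the second sentence says when the target is met. The likely result is more than 150 randomised: 158–188 if 5–20% fail the rule. The natural reading, with all randomised patients in their assigned arm and all available assessments, fits the text and the planned mixed models and gives a sound analysis. Analysts would fill this gap that way without a change to design, sample size or model.

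If only completers were analysed, the expected cost at d=0.49 would be a bias of 0.01–0.06 SD against ketamine on the 24-hour mean and a loss of up to about five points of power on that contrast, or six to seven points on the interaction. Under the shared mechanism this weakens a true effect and does not create a false one. These sizes rest on assumed drop-out rates, slopes and correlations, because the documents give none. The stated detectable effects of 0.49 and 0.57 are correct for 150 analysed.

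### Infusion phase: with two timepoints the time-by-drug test is an unadjusted change-score comparison; constraining baseline means to be equal uses the same data and gains power for moderate effects

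*Combined protocol and SAP*

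**What the plan says.** The Analytic Plan, under Infusion Phase, describes "Mixed models regression with timepoint (baseline, infusion+24-hours) as a continuous within-subject factor, drug condition (ketamine vs. saline) as a fixed between-subject factor", with "subject as a random factor will be applied to test hypothesized time*drug interactions on outcomes". Where an interaction is found, "direction of effects within each drug condition will be disambiguated using baseline vs. post-infusion contrasts". Baseline means are therefore free to differ between arms. The outcome's own baseline value is not a covariate here or elsewhere. The sensitivity analyses at the end of the plan name only sex, age, treatment resistance and concurrent medication.

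Under Power Analyses: "The proposed design will yield 80% power to detect moderate effects based on comparisons of 100 ketamine and 50 saline patients", with d≥.49 at alpha .05. After a further sentence on the three arms of 50, the plan adds: "Power for primary mixed effects analyses comparing treatment groups, which increases with additional repeated measures, will be higher than for such post-hoc single-point contrasts".

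Under Sample Size, enrolment continues until 150 patients "complete, at a minimum, (1) an infusion day, (2) a 24-hour assessment visit", plus at least 75% of training visits. The data collection timeline places an assessment battery before the infusion and repeats it at the 24-hour visit: "depression/emotional functioning assessments, neuroimaging, cognitive tasks)=one visit completed 24-hours after drug infusion".

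**The concern.** With only two timepoints, coding time as continuous changes nothing, and a random subject effect with a free drug effect leaves each patient's change as the sole information on the interaction. Near-complete data are the planned case, because the target 150 must have the 24-hour visit. The baseline is then simply subtracted, which adds noise when it correlates weakly with the 24-hour value.

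At stake is power for moderate effects. The plan declares an interest in moderate to large effects and applies this model to all infusion-phase outcomes. The 24-hour battery includes cognitive tasks, for which no ketamine effect at 24 hours is cited, so those outcomes cannot lean on the d=.80 quoted for depression.

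The sentence on mixed-model power is a lesser matter. It follows the three-arm figure and may refer to the training phase only. The text does not exclude the infusion phase, where the only added measure is the baseline and higher power is not assured.

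**Working it through.** **Inputs.** From the plan: 100 ketamine and 50 saline, alpha .05 (taken as two-sided), d=.49, 80% power, and d=.80 for depression at 24 hours. Assumed, because the documents do not give them: rho, the baseline-to-24-hour correlation; k, the baseline SD divided by the 24-hour SD; and the scale of d.

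**1. The plan's own figure.** For a single 24-hour contrast, d = (1.960 + 0.842) × √(1/100 + 1/50) = 2.802 × 0.1732 = 0.485 (0.488 with the t distribution). Power at d=.49 is 80.3% by noncentral t. The plan's figure reproduces and is a single-timepoint figure.

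**2. Identity.** In three generated data sets, the REML random-intercept interaction and the two-sample t test on change gave the same t values (−3.470, −3.556, −3.435).

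**3. Variances relative to the single 24-hour contrast.**
- Planned (change score): 1 + k² − 2·rho·k, 148 df. This exceeds 1, so power is below the single-point contrast, when rho < k/2.
- Baseline-adjusted: 1 − rho², 147 df.
- Difference: (k − rho)², which is never negative.

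At k=1 and rho=.3, the planned factor is 2 − 0.6 = 1.40 and the adjusted factor is 1 − 0.09 = 0.91.

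**4. Power at d=.49 in 24-hour SD units, noncentral t, 100 versus 50.**

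| rho | Planned, k=1 | Planned, k=0.8 | Planned, k=0.6 | Adjusted, any k | Total N for 80%, k=1: planned / adjusted |
|---|---|---|---|---|---|
| 0.2 | 60% | 69% | 76% | 82% | 240 / 144 |
| 0.3 | 66% | 74% | 80% | 84% | 210 / 138 |
| 0.4 | 73% | 80% | 85% | 87% | 180 / 126 |
| 0.5 | 80% | 87% | 90% | 90% | 150 / 114 |
| 0.6 | 88% | 93% | 94% | 94% | 120 / 99 |
| 0.7 | 95% | 97% | 97% | 98% | 93 / 78 |

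Simulation at k=1 (8,000 runs per rho) gave planned 60/66/73/81/88/95% and adjusted 81/83/87/90/94/97%. Type I error was 4.9–5.2% planned and 4.7–5.4% adjusted.

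**5. If d=.49 is in change-score SD units.** The planned test has 80% throughout. The adjusted factor becomes (1 − rho²)/(1 + k² − 2·rho·k), giving 95/94/92/90/88/86% at k=1, 81–91% at k=0.8 and 80–86% at k=0.6.

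**6. At the cited d=.80, k=1.** Planned power is 90.1% at rho=0 and 97.2% at rho=.3.

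**7. Within-drug contrasts.** Taken from the equal-baseline model over rho 0.2–0.7 (k=1), their standard errors are 2–7% smaller for ketamine and 5–14% smaller for saline than the unadjusted contrasts.

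**8. Unequal slopes by arm.** Relative variance with equal SDs, change score against common-slope adjustment, for ketamine/saline slopes: 0.3/0.7, 0.87 against 0.70; 0.7/0.3, 1.13 against 0.83; 0.5/0, 1.67 against 1.00. At 2:1 allocation the adjusted estimate is no less efficient than either alternative when both slopes lie between 0 and 1.

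**9. Covariance structure.** In 3,000 simulated runs per setting, equal baseline means combined with only the random subject effect gave type I error of 7.8% (k=.7, rho=.4) and 11.4% (k=.5, rho=.4). The unstructured or covariate-adjusted version gave 4.1% and 5.0% in the same settings.

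**10. Training phase.** For 50 versus 50 and d=.57, the treatment effect at 24 hours has 87–94% power with visits on days 1, 5, 12 and 30, against 81% for a single timepoint (assuming compound symmetry, rho 0.7 to 0.3, time coded from 24 hours). The plan's sentence on higher power holds there under those assumptions.

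**The case against.** The planned interaction is a legitimate prespecified test, and at the effects the plan cites for ketamine (d=.80 for depression, above 3 for brain activation) power is already ample. The size of the gain has no anchor in the documents: the widest gaps need equal SDs, a low correlation and d in 24-hour SD units all at once. All of that stands, and it limits the point to efficiency at moderate effects.

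Entry requires MADRS of at least 25, which may narrow the baseline SD and lower rho with it. The table varies k at fixed rho, so for such a scale its gaps can be too wide. As an illustration, take a slope of .5 and a baseline SD cut to 60%. Then k=.65 and rho=.33, and power is 80.3% planned against 84.5% adjusted: 4 points rather than the 10 without selection. With a slope of .3 the gap is still about 7 points. The gain is smaller for such scales but does not reverse.

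The mixed-model power sentence is most naturally read as concerning the training phase. That is a fair reading, and the point does not depend on it.

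Finally, equal expected baselines follow from randomisation, whereas the 150 are defined by completion after randomisation. The constraint is therefore cleanest in all randomised patients. This qualifies how the remedy is applied and does not favour the planned test.

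**Conclusion.** The concern holds as an efficiency point that should be acted on. The planned test is valid but discards information the trial already collects. At d=.49 in 24-hour SD units with equal SDs, adjustment gains about 18 points of power at rho=.3, 10 at .5 and 2 at .7. The gain falls to nil when rho equals k. If d is in change-score units, the planned test shows no shortfall from 80%, and adjustment still reaches 86–95% with equal SDs. Rho, k and the scale of d are assumptions throughout. With a common baseline slope, the most that adjustment can lose, whatever rho and k are, is about one degree of freedom. At d=.80 the practical benefit is small.

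**What to change.** For the infusion phase, fit the mixed model with baseline means constrained equal across arms (no drug effect at baseline) and an unstructured 2x2 covariance. Test the time-by-drug term and take the within-drug baseline-to-24-hour contrasts from the same fit. The unstructured covariance is essential: the constraint should not be combined with the random subject effect alone. An equivalent alternative is to analyse the 24-hour value with the same outcome's baseline as covariate, keeping the within-drug contrasts as follow-up. In two simulated data sets the two approaches gave the same estimates (−0.574 and −0.371), with standard errors within 0.001 of each other. Name the analysis set, preferably all randomised patients.

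Under Power Analyses, either limit the sentence on higher mixed-model power to the training-phase treatment effect, or state the assumed rho, k and scale of d with the resulting infusion-phase power.

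The cost is a dated SAP edit made before unblinded outcome data are seen, and about one degree of freedom. Both batteries are already scheduled, so no visit, measure or patient is added.

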All infusions will be given over 40 minutes and administered in the MUH-CTRC by an experienced team with a linked ACLS-certified code team in a medical hospital setting, with safety/adverse event monitoring sustained for 4-hours post-infusion. Patient safety/decompensation will be monitored at every visit using appropriate exit/referral plans. Patients will be instructed to have nothing by mouth (except for water and coffee) the morning of the infusion and until 2 hours post-infusion.

Randomized, blinded, controlled trials provide the most rigorous method to test intervention effects at any level of analysis. A parallel arm design was selected for primary hypothesis tests due to previously observed cross-over effects in ketamine studies(114) and an anticipated increased risk of unblinding (for both ketamine and CT) if participants can directly compare treatment experiences (e.g., side effects, positive vs. neutral CT stimuli). 2:1 ketamine:saline followed by 2:1 CT:sham randomization was selected to increase probability of benefit to participants(115) and improve recruitment given substantial interest in ketamine from patients and referring clinicians, while maximizing statistical power for key comparisons: ket (n=100) vs. saline (n=50); ket+CT (n=50) vs. ket+sham (n=50) vs. saline+CT (n=50). A 1-month acute follow-up period is feasible and ethical for this initial efficacy study and, if supported, would have a clinically relevant impact, reducing safety and feasibility concerns regarding frequent infusions(28); 12m naturalistic follow-up will further characterize durability and inform frequency for future trials.

Participants will not be withdrawn from existing depression treatments (e.g., medications, therapy). They may continue in existing therapies for the duration of the study, provided they meet all inclusion/exclusion criteria.

Summary of data collection timeline:

The timeline below represents the target day for each set of procedures. At the PI's discretion, the precise day of assessments (e.g., number of days post-infusion) may be adjusted slightly in order to accommodate participant and research facility schedules.

All participants will undergo a medical screening and thorough psychiatric evaluation consisting of a structured diagnostic interview as well as self-report questionnaires to determine eligibility for study participation. Screening assessments for exclusion criteria:

- Initial phone screen

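### The infusion-phase model, read literally, pools the variance of change over 100 ketamine and 50 saline patients; letting it differ by arm is a minor, nearly free improvement

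*Combined protocol and SAP*

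**What the plan says.** Under Analytic Plan, Infusion Phase, the SAP specifies a mixed model with two timepoints (baseline and 24 hours after infusion) and "drug condition (ketamine vs. saline) as a fixed between-subject factor, and subject as a random factor will be applied". The hypothesis test is the time-by-drug interaction. Where that is found, baseline and post-infusion are contrasted within each drug condition to show the direction of effect.

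Allocation to drug is 2:1. Study Design & Methods lists "ket (n=100) vs. saline (n=50)" as a key comparison. Power Analyses bases its detectable effect of d = .49 on "comparisons of 100 ketamine and 50 saline patients" and states: "The proposed design will yield 80% power to detect moderate effects".

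The SAP does not mention a residual variance by arm, a robust standard error, a degrees-of-freedom method or a check of the variances. Neither document gives an SD of change for either arm.

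**The concern.** A model whose only variance terms are a random subject effect and a residual estimates one residual variance from all patients. In a 1:1 trial this is nearly harmless, because the pooled standard error of the difference equals the true one whatever the two variances are. At 2:1 the larger arm dominates the pooled estimate, while the smaller arm contributes more to the true standard error unless the larger arm's variance is at least twice as big.

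So if change is more variable under ketamine, the standard error is too large and the test is conservative, giving up some power. If change is more variable under saline, the standard error is too small and the test rejects too often. The within-arm contrasts have their own problem: each arm's standard error is built from a variance that belongs partly to the other arm.

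**Working it through.** **Inputs from the documents.** n = 100 ketamine and 50 saline; alpha .05; 80% power; detectable d = .49 (all Power Analyses). Earlier studies are said to "report large effects at 24-hours ($d=.80$ for depression". Sidedness is not stated. Two-sided is inferred, because one-sided testing would give 88% power.

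**Assumed input.** R = variance of change under ketamine divided by variance of change under saline, taken as .5, .67, 1, 1.5 and 2. Saline variance is set to 1.

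**Step 1: the plan's own figure.** A two-sided two-sample t-test with 100 and 50, common variance and d = .49 has noncentrality .49/√(1/100 + 1/50) = 2.83 on 148 df, and power 80.3%. The stated 80% reproduces, and it is an equal-variance calculation.

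**Step 2: the planned test is a pooled t on change.** With two timepoints and complete data, the random-intercept interaction test reduces to this. In two simulated data sets the mixed model gave test statistics of −2.394 and −1.207. The pooled t on change gave the same values; the separate-variance t gave −2.389 and −1.308.

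**Step 3: standard error used against the true one.**

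Used: √[((99R + 49)/148) × (1/100 + 1/50)]. True: √(R/100 + 1/50).

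| R | SE used | True SE | Used/true | Real error, common variance | Real error, arm-specific |
|---|---|---|---|---|---|
| .5 | .1413 | .1581 | .894 | .079 | .050 |
| .67 | .1529 | .1634 | .936 | .067 | .050 |
| 1 | .1732 | .1732 | 1.000 | .050 | .050 |
| 1.5 | .2001 | .1871 | 1.070 | .036 | .050 |
| 2 | .2238 | .2000 | 1.119 | .029 | .050 |

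Error rates are simulated from normal change scores. The arm-specific column is the Welch test. At 50 versus 50 the common-variance test stays at about .050 for R = 1 to 2, so the 2:1 allocation is what makes R matter.

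**Step 4: power at d = .49 in average-SD units.** The difference is .49 × √((R + 1)/2), that is .548 at R = 1.5 and .600 at R = 2. Divided by the true SE this is 2.93 and 3.00. The critical value is 1.976 for the arm-specific test (approximately) and 1.976 × (used/true) for the common-variance test.

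- R = 1.5: common Φ(2.93 − 2.11) = .79; arm-specific Φ(2.93 − 1.98) = .83.
- R = 2: common Φ(3.00 − 2.21) = .78 to .79; arm-specific Φ(3.00 − 1.98) = .85.

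Simulation gives .792 and .784 against .828 and .846. At R = 1 it gives .802 against .800, so the arm-specific test costs 0.2 to 0.3 points.

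**Step 5: other scales and the cited effect.**

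- d = .49 in pooled-SD units: common-variance power is about .82 and .83 at R = 1.5 and 2, above the planned 80%.
- Raw difference fixed at .49 saline SDs: the loss against the arm-specific test is about 4 and 9 points. Most of the fall from 80% comes from the larger ketamine SD itself, which no model removes.
- d = .80 in average-SD or pooled-SD units: both tests exceed .99 and differ by about 0.2 points or less.
- Raw difference of .80 saline SDs: the loss is about 0.4 and 1.5 points.

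**Step 6: within-arm contrasts, if taken from the same common-variance model.** The ratio of SE used to true SE is √[(99R + 49)/(148R)] for ketamine and √[(99R + 49)/148] for saline.

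- R = 1.5: ketamine .943 (about 6% too small); saline 1.155 (about 16% too large).
- R = 2: ketamine .914 (about 9% too small); saline 1.292 (about 29% too large).

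By the normal approximation 2[1 − Φ(1.976 × ratio)], the real error of the ketamine contrast is about .062 and .071.

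**The case against.** The case for leaving this alone has real force.

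- **The common variance is inferred.** The SAP is silent on residual structure. A single residual variance is the literal and default reading, not a stated choice, and an analyst could fit arm-specific variances without contradicting the text. This stands, and the point is worded accordingly.
- **There is no evidence of unequal spread.** No SD by arm is given. A reader might cite Exploratory analysis 2 as the plan's own admission that ketamine response varies. It is not: that analysis seeks moderators of the training effect, with post-ketamine measures as candidates, and says nothing about the spread of change from baseline to 24 hours. The sensitivity analyses for moderation by sex, age, treatment resistance and medication cover all hypotheses, so they do allow for drug effects that differ between patients. They are routine, though, and imply no direction or size.
- **The more intuitive direction is the safe one.** If ketamine change is more variable, the interaction test is conservative, so a positive result is not in doubt. Excess false positives in that test require saline to be the more variable arm, and the documents give no reason to expect that. This stands for the interaction, but not for the ketamine contrast in Step 6.
- **The power loss is small on the plan's own terms.** Against the stated 80% it is one to two points in average-SD units and nil in pooled-SD units. At d = .80 it is negligible on either scale. This stands too.

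None of this favours keeping the pooled variance. The alternative costs almost nothing if the variances are equal, and it keeps the error rate at .05 if they are not.

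**Conclusion.** The point holds as a minor, conditional one. Taken literally, the infusion-phase model has a real error of about .036 and .029 at variance ratios of 1.5 and 2, and about .067 and .079 at .67 and .5. An arm-specific variance holds it at .05 and recovers about 4 and 6 points of power at d = .49 in average-SD units for ratios of 1.5 and 2. If ketamine change is the more variable, within-arm contrasts from the same model would overstate the precision of the ketamine change and understate that of the saline change.

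These figures assume complete baseline and 24-hour data, normal change scores, two-sided testing, and variance ratios that the documents do not supply.

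A reader might infer more: that the trial is underpowered, that a positive ketamine result would be unreliable, or that every infusion-phase outcome is affected. The documents support none of these. The stated power reproduces, the conservative direction does not threaten a positive interaction, and an outcome is affected only if its change variances differ between arms, which has not been shown for any of them.

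**What to change.** Add a sentence to the Infusion Phase paragraph of the Analytic Plan: the residual variance, or the two-by-two baseline and 24-hour covariance, is estimated separately by drug condition; degrees of freedom are by Satterthwaite or Kenward-Roger; and the within-arm contrasts come from this same model. The covariance form is the cleaner choice, because with complete data it uses each arm's own variance of change and so matches the separate-variance test checked above.

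The cost is one model option, one SAP sentence and about 0.3 points of power if the variances are equal. Sample size, data collection and conduct do not change. The change should be made before the data are unblinded.
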